Net benefits. Resource utilization and cost data will be used to estimate mean net benefit (benefits – costs) per patient in each group from agency and societal perspectives (Drummond et al, 2005; Zarkin et al., 2008). Mean net benefits, and confidence intervals around estimates, then will be calculated by subtracting mean net benefit of reinforcement conditions from standard care. Finally, sensitivity analyses (Olmstead et al., 2007a; Drummond et al., 2005) will determine the robustness of the net benefit to alternative assumptions about a variety of cost parameters (e.g., unit costs of services, reimbursements received).

Cost-effectiveness ratios. If the interventions engender net benefits (as they have been shown to in the context of substance abuse treatment; Lott & Jencius, 2009), then they ought to be adopted. Even in the absence of a net benefit, the incremental cost-effectiveness ratio (ICER) is critical to policy decisions. The ICER is calculated as: (i) incremental costs to (ii) incremental effectiveness (difference between average effectiveness of treatments in terms of days abstinent or employed). Using expert panel recommendations (Gold, 1996; Johannesson, 1996; Weinstein, 1996), we will present traditional ICERs and uncertainty of the ratios (Gold, 1996; O'Brien et al., 1994) and derive a single synthetic measure of multiple indicators of effectiveness, including quality of life (Hargreaves et al., 1997; Rosenheck et al., 1998). We will also conduct acceptability curve analysis to provide policy relevant interpretations (Fenwick et al, 2001,2004; Lothgren & Zethraeus, 2000; Polsky et al., 1997; vanHout et al., 1994). Multiple samples are selected randomly (bootstrapped), with replacement, from the original sample to approximate the larger population. Incremental cost and effectiveness values and ICERs can be calculated for each new sample and compared with theoretical "willingness to pay" values for an outcome, such as days without drinking or days employed. Such analyses inform policy makers in decision-making (Olmstead et al, 2007ab; Sindelar et al, 2007b) and can be conducted with samples even smaller than those herein (Olmstead et al., 2007c,2009; Sindelar et al., 2007a).

This study allows for rigorous determination of costs and benefits of interventions that accrue to unemployment service agencies and society more generally. A provider perspective is crucial because, at least in the immediate future, agencies are unlikely to fund expanded services unless they are cost beneficial. Societal perspectives (ICER analyses) are critical for future policy that might allocate state and federal funding to support reinforcement interventions, as is now being done for substance abuse services ([name] et al., in press b) as well as in other health care arenas (National Business Group on Health, 2013). Only a comprehensive study such as this can address multiple perspectives and extend

them to clinically and socially relevant settings and populations.

Future directions: If the dual reinforcement intervention yields the best outcomes and is cost-effective, then that approach should be adopted clinically. If reinforcing job-related activities alone increases job attainment even without reducing drinking, this approach may be expanded to other unemployed groups, including those without drinking problems; if it fails to improve outcomes, other approaches are needed to improve transition to re-employment. Likewise, reinforcing negative BrACs may only reduce drinking but not improve employment outcomes; this BrAC reinforcement approach then may be useful for other populations with hazardous drinking (e.g., college students, patients in medication trials), but not specifically the unemployed. Regardless of outcomes, this study is likely to guide future research and practice in assisting unemployed persons and hazardous drinkers. Importantly, these groups, both independently and collectively, represent a sizeable proportion of US society, and they experience significant—yet preventable— morbidity and mortality.

Human Subjects

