Interventions for Unemployed Hazardous Drinkers

NCT02559609

Protocol V. 6/21

PROTOCOL: Interventions for unemployed hazardous drinkers

PRINCIPAL INVESTIGATORS: [name], and [name]

Despite recent improvements in the US economy, unemployment remains a significant concern, and estimates indicate that one-third of unemployed persons drink at hazardous levels, adversely impacting their health and abilities to find jobs. Reinforcement interventions are highly efficacious in reducing substance use, and they can be applied to increase job-seeking activities as well. In partnership with CT United Labor Agency, this project is designed to reduce hazardous drinking and enhance active participation in job-seeking activities among those with job loss. It will evaluate the independent and combined effects of reinforcing negative breathalyzer samples and job-seeking activities to ascertain the simplest and most cost-effective approach to improving outcomes in this population. Unemployed individuals with hazardous drinking ($N = 280$) will be randomly assigned to one of four conditions using a 2×2 design: standard care, standard care with reinforcement for submitting negative breathalyzer samples, standard care with reinforcement for job-seeking activities, or standard care plus reinforcement for both negative breathalyzer samples and job-seeking activities. Participants in all conditions will receive usual services part of CT United Labor Agency, along with a novel remote breath alcohol monitoring procedure. The study interventions will be in effect for three months, and participants will be followed for one year. Alcohol and other drug use, employment, psychiatric symptoms, and global measures of health will be assessed throughout treatment and follow-up. Reinforcing negative breathalyzer samples is expected to significantly reduce drinking, and reinforcing job-seeking activities is expected to increase re-employment rates and reduce time until job attainment. Reinforcing both negative breathalyzer samples and job-seeking activities is hypothesized to improve outcomes along both domains. The reinforcement interventions may also decrease psychiatric distress and slow progression of physical decline, common among the unemployed. If efficacious and cost-effective, results from this study may stimulate adoption of reinforcement interventions in the context of unemployment services. Reducing the adverse consequences of hazardous drinking and improving job re-entry may have pronounced benefits in a highly vulnerable segment of the US population.

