Additionally, this study will estimate the costs and cost-effectiveness of the reinforcement interventions relative to usual care. If they increase the proportion of individuals who transition to re-employment and reduce time to job attainment, reinforcement interventions may be cost-effective and ultimately integrated in the context of unemployment services. Importantly, reinforcement interventions are now being applied nationwide in the context of substance abuse treatment services ([name] et al., in press b) as well as in other health care arenas (National Business Group on Health, 2013). These dissemination experiences bode well for their ultimate adoption in the context of unemployment services, if benefits are found in this study.

Significance

The unemployment rate in the US remains 7.7% (Bureau of Labor Statistics, 2013), and this rate disguises a larger change in employment patterns, in which precarious or impermanent jobs, that encompass a triad of contingent duration of employment, absence of benefits, and reduced compensation, are increasing (Kalleberg et al., 2000). In part because of this trend, our nation is experiencing the highest poverty level since the early 1980s (Danziger et al., 2012), with a 45% increase in food stamp program enrollment between 2009 and 2012 (Tavernise, 2012). Health disparity groups, including racial/ethnic minorities and those with substance use problems, are most impacted by job loss and unemployment.

Recent data from the National Survey on Drug Use and Health (SAMHSA, 2011) indicate that 33.2% of the unemployed binge drink, and 14.8% have an alcohol use disorder, nearly double the rate of employed persons. The loss of a job, especially involuntary job loss, results in substantial financial, family, and personal stress, along with an increase in unstructured time, all of which can impact alcohol use (Forcier, 1988). Most cross-sectional studies have found greater frequency of hazardous drinking in unemployed versus employed samples (Bolton & Rodriguez, 2009; Dooley & Praise, 1998; Khalt et al., 2004; Mulia, et al., 2013). Longitudinal studies likewise demonstrate that loss of employment can result in greater alcohol consumption and problems (Catalano et al., 1993; Claussen, 1999; Davalos et al., 2012; Mossakowski, 2008; Popovici & French, 2013; Thomas et al., 2005), particularly among men (Virtanen et al., 2008; Deb et al., 2011) and individuals with lower educational attainment (Deb et al.,

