Economic Evaluation. If primary aims are supported, we will conduct cost-effectiveness analyses.

These interventions can be costly, and not only must costs of reinforcers be included, but so must administration costs, which include staff time for managing and delivering reinforcers. Despite costs, these interventions may provide benefits to society in terms of increased productivity and reduced healthcare service utilization (hospitalizations, ER visits). This study will estimate costs of these reinforcement interventions and determine their net benefit in terms of improving both drinking and employment outcomes.

a. Comprehensive administrative costs of interventions will be quantified (Olmstead et al, 2007abc; Rosenheck et al, 1995; Sindelar et al. 2007ab), including costs of prizes, mileage for purchasing them, BrAC testing and management (personnel time to arrange and review videos, and cell phones costs in Groups B and D), and setting and verifying job-related activities (Groups C and D only). Costs related exclusively to data collection will not be included (i.e., cell phones and staff salary for collection and viewing BrAC videos when not reinforced in Groups A and C). Costs for usual employment and clinical services, and reimbursement for same when applicable, will be ascertained.

b. General healthcare costs will be estimated by multiplying service units used by average unit costs. In- and out-patient, day hospital, aftercare and emergency room services will be estimated from CT claims data, and nationally from the Market Scan database, which estimates service costs.

c. Societal costs will be obtained on productivity (days worked, earnings, and workdays affected by substance use), automobile crashes (including property damage, injuries, and fatalities), and criminal justice system costs. Participants receiving reinforcement interventions may have reduced societal costs, and the SU collects data on these variables, police contacts, court hearings, and incarceration, along with timing of events that resulted in criminal justice service use so acts occurring before study participation can be separated from those occurring during it in terms of resource utilization. Unit costs of services will be estimated from national reports (Pastore & Maguire, 2003; US Dept. of Justice 2006).

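### Usual care is the only economic comparator the plan names, and no four-arm incremental comparison, with its uncertainty and a decision rule, is specified to test the combined arm's added cost over a single reinforcer

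*Combined protocol and SAP*

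**What the plan says.** The opening summary gives the purpose of the 2×2 design as "to ascertain the simplest and most cost-effective approach to improving outcomes in this population". The Specific aims then set the economic comparison: "this study will estimate the costs and cost-effectiveness of the reinforcement interventions relative to usual care".

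The Economic Evaluation section is conditional: "If primary aims are supported, we will conduct cost-effectiveness analyses". Its Net benefits paragraph estimates mean net benefit "per patient in each group from agency and societal perspectives". The differences and their confidence intervals are then "calculated by subtracting mean net benefit of reinforcement conditions from standard care".

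The Cost-effectiveness ratios paragraph defines the ICER as incremental cost over the "difference between average effectiveness of treatments in terms of days abstinent or employed". It plans bootstrapped ICERs and acceptability curves. It names no pairs of arms, no ordering by cost and no dominance rule.

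Two statements turn results into recommendations. The Cost-effectiveness ratios paragraph says that interventions yielding net benefits should be taken up. Future directions says: "If the dual reinforcement intervention yields the best outcomes and is cost-effective, then that approach should be adopted clinically". Neither names a comparator.

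**The concern.** The four arms are mutually exclusive: an agency can give a client one of them. When exclusive options are compared, the question for the combined arm is whether its extra effect over the next cheaper worthwhile option (Group B or C) justifies its extra cost. A comparison of D with A averages the first step (A to a single reinforcer) with the second (a single reinforcer to both). If the second step buys less than the first, that average hides it.

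B, C and D could all show a net benefit against usual care, and the adoption statement in the Cost-effectiveness ratios paragraph would then support all three without choosing among them. The Future directions statement adds that D must give the best outcomes, but that condition compares effects and does not bear on added cost. At stake is the recommendation that agencies and policy makers would take from the trial: D could be endorsed against usual care when a single reinforcer is the better use of the money.

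**Working it through.** **Inputs from the plan (Group B, C and D descriptions).** Maximum draws: B 266 on average, C 270, D 536. The bowl has 500 slips: 164 small (up to $1), 35 large (up to $20), 1 jumbo (up to $100), the rest without a prize.

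**Reproducing the draw totals** (weekly base draws plus capped bonuses over 12 weeks):
- C: 12×9 + (6+8+10+12+14+7×16) = 108 + 162 = 270, as stated.
- B: 12×10 + (5+7+9+11+13+7×15) = 120 + 150 = 270, against 266 stated, a difference of 1.5%. The stated 266 is used below.
- D: 266 + 270 = 536, as stated.

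**Maximum expected prize cost.** Value per draw = (164×$1 + 35×$20 + 1×$100)/500 = $1.928.
- B: 266 × 1.928 = $512.85
- C: 270 × 1.928 = $520.56
- D: 536 × 1.928 = $1,033.41

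D therefore adds $520.56 over B and $512.85 over C.

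**Illustration.** The documents give no effect on employed days and no willingness to pay. Assume that C gains 20 employed days over A, that D gains 20 + x, that a day is worth $60, and that prizes are the only cost. C v A is then 520.56/20 = $26.0 per day throughout.

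- D v A = 1,033.41/(20 + x)
- D v C = 512.85/x
- Net benefit over A: C = 60×20 − 520.56; D = 60×(20 + x) − 1,033.41

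| x (days D adds over C) | D v A, $/day | D v C, $/day | Net benefit C | Net benefit D |
|---|---|---|---|---|
| 20 | 25.8 | 25.6 | $679 | $1,367 |
| 10 | 34.4 | 51.3 | $679 | $767 |
| 5 | 41.3 | 102.6 | $679 | $467 |
| 2 | 47.0 | 256.4 | $679 | $287 |
| 0 | 51.7 | D dominated | $679 | $167 |

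**Where the two comparisons disagree.** At $60, D passes against A if 20 + x exceeds 1,033.41/60 = 17.2, so for every x from 0 upward. It passes against C only if x exceeds 512.85/60, about 8.5. The answers conflict for x from 0 to about 8.5.

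Varying the assumed value of a day:
- At $40, D passes against A when x exceeds 1,033.41/40 − 20 = 5.8, and against C when x exceeds 512.85/40 = 12.8. The conflict runs from about 5.8 to 12.8.
- At $100, D always passes against A, and against C when x exceeds 5.1. The conflict is below about 5.1.

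**What the planned quantities already give.** NB_D − NB_C = (NB_D − NB_A) − (NB_C − NB_A). The arm-level net benefits therefore rank all four arms as point estimates. At x = 5 they put C ($679) above D ($467). The interval for D v C cannot be read off the two planned intervals, because both differences share Group A.

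**The case against.** A reader might infer that the arms are never compared incrementally, or that the plan cannot identify the most cost-effective arm. The documents do not support either reading. Net benefit is to be estimated in each group, and ranking those values gives the same point decision as a full incremental analysis at the same valuation. The ICER definition speaks of treatments in general, and the bootstrap and acceptability text names no single comparator, so D v B or D v C is open to the analyst.

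A reader might also infer that the plan necessarily favours D. That depends on diminishing returns. Aim 3 looks for synergy, and at x = 20 the two ratios agree ($25.8 and $25.6). The illustration counts employed days alone, while D also reinforces negative breath tests and the plan intends a combined effectiveness measure. That omission works against D.

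The dollar figures are ceilings: prize values are maxima, prizes are bought in bulk or on sale, and full adherence is assumed. In the other direction, the administrative cost list charges D with both breath-test management and activity verification, which prize costs leave out.

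Finally, the economic evaluation is conditional and supplementary, Future directions is narrative, and the design rationale (Why 4 conditions?) already values a simpler intervention if one target is enough.

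All of this stands, and it narrows the point. It does not supply the missing contrast, its interval, or a rule that uses them. Pairs left unnamed can also be chosen after the results are seen.

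**Conclusion.** The concern holds in limited form. Usual care is the only comparator named for cost-effectiveness and for the net-benefit differences with intervals, and neither adoption statement asks whether D's added cost over B or C is justified. A point ranking of the four arms is derivable; a prespecified incremental contrast, its uncertainty and a decision rule are absent.

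At maximum prize values and full adherence, D costs about twice a single arm ($1,033 against $513 to $521). With an assumed 20 days gained by C and an assumed $60 per day, the stated comparison passes D while the incremental one fails it for any gain over C below about 8.5 days. The conflict disappears when the second reinforcer adds to the first at a comparable size, as with additive gains of that order or with synergy. The range moves with the assumed value of a day, and the figures show that the answer can reverse, not that it will. No primary result or data collection is affected. This is a cheap improvement.

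**What to change.** In the Net benefits and Cost-effectiveness ratios paragraphs, keep usual care as the reference arm and add:

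1. Order A, B, C and D by mean cost and remove dominated and extendedly dominated arms. Report each remaining arm's ICER and net-benefit difference, with its interval, against the next cheaper remaining arm.
2. Present acceptability curves as the probability, at each willingness to pay, that each of the four arms has the highest net benefit.
3. Word the adoption statements in Cost-effectiveness ratios and Future directions so that they rest on these results.

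The cost is some plan wording and a little more analysis of the same data. The downside is that D's ratio may look less favourable than it does against usual care.
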